### ***Up-titration of anakinra during CRS and ICANS***

Given the high variance in the degree of systemic inflammation observed across patients during CRS and ICANS, we hypothesize a two-step, clinically driven, up-titration of the anakinra dose will decrease CRS/ICANS severity and accelerate symptom resolution. Up-titration of anakinra has been previously reported to treat CRS or ICANS, and secondary HLH. Details regarding up-titration of the anakinra dose are provided in Section 6.1.

## **2.5 Rationale for the use of a single CD19 CAR T-cell product**

Pivotal clinical trial data suggest significant differences in the incidence and severity of CRS and ICANS across FDA-approved CAR T-cell products. Since this is a pilot study with limited sample size, we will restrict the inclusion criteria to patients treated with liso-cel to analyze a population with a more homogeneous risk of CRS/ICANS.

## **3.0 STUDY OBJECTIVES AND ENDPOINTS**

### **3.1 Primary Objective**

Decrease the incidence of CRS by day 28 after liso-cel treatment for B-NHL.

### **3.2 Secondary Objectives**

1. Decrease the severity of CRS by day 28 after liso-cel treatment .
2. Decrease the incidence and severity of neurotoxicity by day 28 after liso-cel treatment.
3. Decrease the rate and duration of hospitalization
4. Decrease corticosteroid usage after liso-cel treatment
5. Evaluate safety of anakinra use after CAR-T cell infusion.
6. Evaluate the effect of anakinra on liso-cel efficacy for treatment of B-NHL, as evaluated at approximately day 28 and day 90 after treatment.

### **3.3 Exploratory Objectives**

1. To assess the pharmacokinetics of anakinra in B-NHL patients undergoing treatment with liso-cel
2. To evaluate the effects of anakinra on the immune system (e.g., CAR T cells in vivo kinetics, other immune cells, serum cytokine concentrations)

### **3.4 Primary Endpoint**

Absence of any grade CRS

### 3.5 Secondary Endpoints

- Peak CRS grade according to the 2019 American Society for Transplantation and Cellular Therapy (ASTCT) consensus criteria within 28 days after liso-cel infusion. CRS will also be graded according to the 2014 NIH criteria to allow comparisons to historical controls.
- Peak ICANS grade according to the 2019 ASTCT consensus criteria within 28 days after liso-cel infusion. ICANS will also be graded according to the NCI CTCAE Version 5.0 to allow comparisons to historical controls.
- Rate and duration of hospitalization after liso-cel treatment.
- Cumulative corticosteroids dose within 28 days after liso-cel infusion.
- Adverse events (AEs) according to the NCI CTCAE Version 5.0 within the first 28 days after liso-cel administration.
- Disease response to CAR T-cell therapy approximately 28 days and 90 days after CAR T-cell infusion according to the Lugano criteria.

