### 1.2 Significant toxicities after CD19 CAR T-cell therapy in patients with R/R B-cell NHL

The promising results of CD19 CAR-T cell therapy in R/R B-cell NHL are tempered by two potentially life-threatening toxicities: CRS and ICANS. The incidence, severity, and timing of CRS and ICANS across pivotal trials and non-trial settings are detailed in Table 1. Higher incidence of severe CRS and ICANS have been reported after axi-cel and brexu-cel treatment compared to tisa-cel and liso-cel. While the most favorable toxicity profile has been observed after liso-cel, 42% and 30% of patients treated on the TRANSCEND clinical trial still experienced any grade CRS and ICANS, respectively.

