**Table 1. CRS and ICANS after CD19 CAR T-cell therapy for R/R LBCL**

	Axi-cel			Brexu-cel	Tisa-cel	Liso-cel
	ZUMA-1 	Nastoupil et al 	Jacobson et al 	ZUMA-2 	JULIET 	TRANSCEND 
No. of patients treated	101	275	122	60	93	269
CRS (graded according to the 2014 Lee criteria for all studies except JULIET*)						
Any grade / ≥ grade 3	93 % / 11%	91% / 7%	93% / 16%	91%/15%	58%/22%	42%/2%
Median time to onset, range	2 days (1-12)	NR	3 days (0-20)	3 days (1-13)	3 days (3-9)	5 days (1-14)
Median duration, range	8 days (NR)	NR	6 days (1-27)	10 days (1-50)	7 days (2-30)	NR
ICANS (graded according to the CTCAE 4.03)						
Any grades / ≥ grade 3	64 % / 28%	69% / 31%	70% / 35%	63%/31%	21%/12%	30%/10%
Median time to onset, range	5 days (1-17)	NR	5 days (0-34)	6 days (1-32)	6 days (1-17)	9 days (1-66)
Median duration, range	17 days (NR)	NR	7 days (1-52)	21 days (2-454)	14 (NR)	NR

Abbreviations: Axi-cel, axicabtagene ciloleucel; brexu-cel, brexucabtagene autoleucel; tisa-cel, tisagenlecleucel; liso-cel, lisocabtagene maraleucel; CRS, cytokine release syndrome; ICANS, immune effector cell-associated neurotoxicity syndrome; NR, not reported. \*CRS graded using the PENN scale.

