### 11.3 Grading of the Severity of an Adverse Event

AEs will be graded in severity according to the NCI Common Terminology Criteria for Adverse Events (CTCAE) Version 5.0. If a CTCAE criterion does not exist, the investigator should use the grade or adjectives: Grade 1 (mild), Grade 2 (moderate), Grade 3 (severe), Grade 4 (life-threatening), or Grade 5 (fatal) to describe the maximum intensity of the adverse event. CRS will be graded according to the 2019 ASTCT consensus criteria (Appendix A) and the 2014 NIH Lee criteria (Appendix B), the latter to allow for comparisons with historical controls. ICANS will be graded according to the 2019 ASTCT criteria (Appendix C) and the CTCAE 5.0, the latter to allow for comparisons with historical controls. In addition, therapeutic interventions related to CRS and ICANS management will be recorded.

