### **12.1 Primary endpoint:**

We will assess the efficacy of anakinra in preventing the occurrence of any grade CRS using the Bayesian optimal phase 2 (BOP2) design  with a planned interim analysis after 15 patients are treated ( $n$ , interim sample size). Unlike other existing Bayesian designs, the BOP2 design explicitly controls the type I error rate, thereby bridging the gap between Bayesian designs and frequentist designs.  $N$  denote the maximum sample size.

Based on the TRANSCEND clinical trial data in LBCL patients, the incidence of any grade CRS liso-cel therapy is estimated to be approximately 40%. Let  $p_{eff}$  denote the proportion of patients without any grade CRS (efficacy) and define the null hypothesis  $H_0: p_{eff} \leq 0.6$ , representing that the treatment is inefficacious. We assume a vague Beta(0.6,0.4) prior distribution for  $p_{eff}$ . Let  $y$  be defined as the absence of any grade CRS and the posterior probability will be computed as follows using 100,000 simulations:

$$Pr_{eff} = Pr(p_{eff} | y, n) = Beta(p_{eff} | y + 0.6, n - y + 0.4)$$

This primary endpoint will not be met if

$$Pr(p_{eff} > 0.6 | data) < \lambda \left(\frac{n}{N}\right)^\alpha,$$

where  $\lambda=0.9$  and  $\alpha=0.51$  are design parameters optimized to minimize the chance of incorrectly claiming that an efficacious treatment is not promising (i.e., type II error) under the alternative hypothesis  $H_1: p_{eff} = 0.85$ , while controlling the type I error rate (i.e., the probability of incorrectly claiming that the treatment is acceptable under  $H_0$ ) at 0.1. This design yields a statistical power of 0.928 under  $H_1$ .

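### ICANS is graded with CTCAE 5.0 for historical comparison, but the only historical ICANS data with a stated scale were graded with CTCAE 4.03

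*Combined protocol and SAP*

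**What the plan says.** Section 3.5 makes peak ASTCT 2019 grade within 28 days the ICANS endpoint and then adds: "ICANS will also be graded according to the NCI CTCAE Version 5.0 to allow comparisons to historical controls". Section 11.3 has the same rule: "ICANS will be graded according to the 2019 ASTCT criteria (Appendix C) and the CTCAE 5.0, the latter to allow for comparisons with historical controls". Neither section gives any other purpose for the CTCAE grading of ICANS.

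The published toxicity data are in Table 1 of Section 1.2, which covers six studies of four CAR T-cell products. The heading of its ICANS block says the events were "graded according to the CTCAE 4.03" and lists no exception. The liso-cel column, from the TRANSCEND trial, gives ICANS in 30% of patients at any grade and 10% at grade 3 or higher. The text of Section 1.2 repeats the any-grade figures: "42% and 30% of patients treated on the TRANSCEND clinical trial still experienced any grade CRS and ICANS, respectively".

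Section 2.3.2 gives a second comparator: patients at the same institution who received liso-cel without prophylactic anakinra, with ICANS in 27%. Neither the ICANS scale nor the size of that cohort is stated. The documents do not define the term historical controls.

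**The concern.** Reducing the incidence and severity of neurotoxicity is secondary objective 2 (Section 3.2). The trial has one arm, so a reduction can only be judged against outside data. The second ICANS grading is there to make that possible, yet it uses a different CTCAE version from the only outside data whose version is given.

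ICANS has also already carried weight. Section 12.3 allows expansion to be decided on primary and secondary endpoints together, and its February 2023 update cites ICANS in 3 of 15 patients among the reasons for treating 10 more. If the final report sets ICANS rates beside the pivotal liso-cel rates, a reader will want to know that both were graded in the same way.

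**Working it through.** The check is mainly a comparison of text.

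**Planned scale against historical scale**

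| Toxicity | Supplementary scale for historical comparison (3.5, 11.3) | Scale stated in Table 1 | Match |
|---|---|---|---|
| CRS | 2014 NIH criteria | Same criteria, one study excepted (not the liso-cel trial) | Yes |
| ICANS | CTCAE 5.0 | CTCAE 4.03, no exception listed | No |

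The CRS row matters for interpretation. For CRS, the scale chosen for historical comparison is the one Table 1 reports. Section 12.1 also takes its CRS benchmark of about 40% from the liso-cel trial in that table. Both facts support reading Table 1, and its liso-cel column in particular, as at least one intended historical control. Only the ICANS row is out of line. Nothing in the documents calls the two CTCAE versions interchangeable for ICANS, plans a 4.03 grading, or plans to regrade historical data.

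**Size**

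The plan states no figure that depends on the CTCAE version, so there is none to reproduce. Sampling error gives the context.

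- Inputs: 3 of 15 patients with ICANS (Section 12.3), all grade 3 or higher (Section 2.3.2). The scale used for these grades is not stated.
- Observed rate: 3/15 = 20%, both at any grade and at grade 3 or higher.
- Exact 95% limits: the lower is the 0.025 quantile of Beta(3, 13) = 4.3%; the upper is the 0.975 quantile of Beta(4, 12) = 48.1%.
- Benchmarks: 30% any grade and 10% grade 3 or higher (Table 1); 27% any grade (institutional cohort). All three lie inside 4.3% to 48.1%.
- If the rate stayed at 20% in 25 patients, 5/25 has exact 95% limits of 6.8% and 40.7%, which still contain all three.

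Moving one patient across a grade boundary shifts a rate by 1/25 = 4 points, 1/15 = 6.7 points or 1/10 = 10 points. That holds for any endpoint in a trial of this size. It does not show that any patient would move.

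**Can ICANS be regraded?**

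Section 11.2 collects all AEs of grade 3 or higher, plus grade 1-2 neurologic symptoms that contribute to the diagnosis and grading of ICANS. Section 11.3 adds the related interventions. The material for a 4.03 grading should therefore largely exist. One caution is that Section 11.2 also asks for the diagnosis, rather than its separate signs, to be recorded as the event. Symptom-level detail may then have to come from the medical record for some patients.

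**The case against.** The strongest reply is that the protocol never says Table 1 is the historical control for ICANS. The table sits in the background and spans several products, and Section 2.5 says toxicity risk differs between products. Section 12.1 uses the pivotal liso-cel trial as a benchmark for CRS, not for ICANS. The only ICANS comparison the protocol actually makes with its own result is with the institutional cohort (20% against 27%), whose scale could be ASTCT, 4.03 or 5.0. This stands: a reader might infer that the historical controls as a whole were graded with 4.03, and the documents do not support that. They support it only for the Table 1 data.

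Second, no harm is shown. A reader might infer that a difference from the benchmark would be confounded by CTCAE version. That requires the relevant neurological terms to be graded differently in the two versions, and nothing in the documents shows that they are. This also stands. What remains is that comparability is the stated purpose and the plan neither secures nor justifies it.

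Third, no planned decision depends on this grading. ASTCT 2019 is the main scale, Section 12.3 plans descriptive summaries with exact intervals and no test against historical ICANS data, and neither the primary rule nor the stopping rules in Section 12.4 use it. This is correct and limits the weight of the point.

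Finally, a reader might infer that 5.0 should simply be replaced by 4.03. If the institutional cohort is the intended control and was graded with 5.0, that would create a mismatch. The sound remedy is to add 4.03, not to substitute it.

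**Conclusion.** The point holds in a limited form. A supplementary ICANS grading whose only stated purpose is historical comparison uses CTCAE 5.0, while the only historical ICANS data with a stated scale, including the liso-cel pivotal trial, are on CTCAE 4.03. The mismatch appears in both places where the rule is stated, and the parallel CRS rule does not share it.

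The size and direction of any effect on ICANS rates cannot be determined from the documents. At 15 to 25 patients, sampling error is wide whichever version is used. The primary endpoint, decision rule and stopping rules do not change. This is a minor improvement to the interpretation of a secondary objective.

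The conclusion rests on one inference: that the Table 1 liso-cel data are among the intended historical controls for ICANS. The matching CRS scale and the benchmark in Section 12.1 support that inference, but the protocol does not state it.

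**What to change.** In Sections 3.5 and 11.3, with the same wording in both:

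- Add grading of ICANS under CTCAE 4.03, derived from the symptoms already recorded and covering the first 15 patients as well as the expansion cohort. Use it for any comparison with the Table 1 liso-cel rates.
- Keep ASTCT 2019 as the main ICANS scale and CTCAE 5.0 as already planned.
- Name the historical control for ICANS. If the institutional cohort treated without anakinra is used, state the scale on which its 27% was graded and compare on that same scale.

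The cost is a short wording change and the regrading of a few events (3 of the first 15 patients had ICANS), with recourse to the medical record where the case report form holds only the diagnosis. No sample size, decision rule or visit schedule changes. The fix aligns the version only; a comparison with another trial's patients remains descriptive.

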### 3.6 Projected Target Accrual

[figure not shown]
Table 1: Targeted / Planned Enrollment			
Ethnic Category	Patient Numbers		
	Females	Males	Total
Hispanic or Latino	0	0	0
Not Hispanic or Latino	10	15	25
Ethnic Category Total of All Subjects	10	15	25
Racial Category			
American Indian / Alaska Native	0	0	0
Asian	0	0	0
Native Hawaiian or Other Pacific Islander	0	0	0
Black or African American	0	0	0
White	10	15	25
More than One Race	0	0	0
Racial Categories: Total of All Subjects	10	15	25

## 4.0 STUDY DESIGN AND INVESTIGATIONAL PLAN

### 4.1 Overall Study Design

Phase 2 single-center pilot study to evaluate the efficacy and safety of anakinra to prevent liso-cel-related CRS and neurotoxicity

### Figure 1. Study Schema

### 4.2 Protocol Enrollment

Enrollment is expected to take approximately 2 years. Disease restaging should be performed per standard of care approximately 28 and 90 days after liso-cel infusion. The study team may contact the local oncologist office by a letter/phone call to request the results of the day 90 restaging.

## 5.0 STUDY POPULATION

The target study population consists of adult patients with B-NHL receiving treatment with liso-cel. Patients must meet all of the inclusion criteria and have none of the exclusion criteria to be enrolled in this study.

### 5.1 Inclusion Criteria

Results of tests and/or procedures conducted as per standard of care purposes may be used for research purposes if conducted within the protocol-defined window prior to screening/leukapheresis and/or T-Cell Therapy.

- 1) Subjects must be 18 years of age or older.
- 2) Karnofsky performance status of  $\geq 60\%$ .
- 3) Patients with B-NHL and eligible for treatment with liso-cel. Patients treated with non-conforming (out-of-specification) liso-cel may remain on study.
- 4) Negative serum pregnancy test within 2 weeks of enrollment for women of childbearing potential, defined as those who have not been surgically sterilized or who have not been free of menses for at least 1 year.
- 5) Fertile male and female subjects must be willing to use an effective contraceptive method before, during, and for at least 4 months after the last dose of anakinra.
- 6) Ability to understand and provide informed consent.

### 5.2 Exclusion criteria

- 1) Subjects requiring ongoing daily corticosteroid therapy at a dose of  $>15$  mg of prednisone per day (or equivalent). Pulsed corticosteroid use for disease control is acceptable.
- 2) Active autoimmune disease requiring immunosuppressive therapy is excluded unless discussed with the PI.
- 3) Known hypersensitivity to E coli-derived proteins, anakinra, or to any component of the product.
- 4) Major organ dysfunction defined as:

- a. Serum creatinine > 2.5 mg/dL
- b. Significant hepatic dysfunction (Alanine aminotransferase (ALT) and aspartate aminotransferase (AST) > 5x upper limit of normal; bilirubin > 3.0 mg/dL) unless due to malignancy or Gilbert's syndrome in the opinion of the PI or designee.
- c. Subjects with clinically significant pulmonary dysfunction, as determined by medical history and physical exam should undergo pulmonary function testing. Those with an FEV1 of < 50 % of predicted or DLCO (corrected) < 40% will be excluded.
- d. Significant cardiovascular abnormalities as defined by any one of the following:  
NYHA class III or IV congestive heart failure, clinically significant hypotension, uncontrolled symptomatic coronary artery disease, or a documented ejection fraction of <35%.

5) Uncontrolled serious and active infection.

### **5.3 Reproductive Potential and Contraception Requirements**

Pregnancy test for females of reproductive potential must be negative within 2 weeks before enrollment. Any female patient who does not meet at least one of the following criteria will be considered to have reproductive potential:

- Post-menopausal for at least 12 consecutive months (i.e., no menses), or
- Undergone a sterilization procedure (hysterectomy, salpingectomy, or bilateral oophorectomy; tubal ligation is not considered a sterilization procedure)

Female subjects with reproductive potential who are not sexually abstinent and male subjects who are sexually active with females of reproductive potential must agree to use a suitable method of contraception for the duration of the study and for at least 4 months after the last dose of anakinra, for example:

- Condom with spermicidal agent
- Diaphragm or cervical cap with spermicidal agent
- Intrauterine device
- Hormonal contraceptives in combination with either a condom, diaphragm, or cervical Cap

## **6.0 TREATMENT PLAN**

### **6.1 Anakinra Treatment**

#### **Prophylactic dose:**

Anakinra 200 mg will be diluted in 200 mL of sodium chloride 0.9% and administered IV over approximately 10-30 minutes once daily (approximately every 24 hours,) for 14 days, with the first dose administered 2-4 hours before liso-cel infusion (day 0 through day 13). Scheduling variations in the timing of anakinra administration are acceptable, e.g., in case of clinical events (e.g., unplanned hospitalization) or if changes to the patient's schedule occur. The anakinra dose may be modified or held at the discretion of the PI or designee (e.g., in case of severe and/or uncontrolled infection). Should patients receive the first dose of anakinra but do not receive liso-cel for any reason, they may be re-treated with anakinra if liso-cel is given at a later point.

Anakinra dose modification: in patients with severe renal insufficiency or end-stage renal disease, defined as CrCl less than 30 mL/min, anakinra will be administered every other day instead of every day. Local injection-site reactions should be managed per institutional standards.

#### **Up-titration in case of CRS or ICANS:**

[figure not shown]
Step 1 (8 mg/kg/day): In patients who develop CRS or ICANS during anakinra prophylaxis at 200 mg/day, anakinra will be increased to 8 mg/kg/day. The step 1 anakinra dose will be calculated using the participant's actual or ideal body weight as per PI discretion. The total daily dose will be divided over three doses in 24 hours, each dose will be rounded to the nearest 100 mg, and diluted in NaCl 0.9% at a volume sufficient to achieve a goal concentration of 1 mg/ml, and given IV over approximately 10-30 minutes. Once CRS and ICANS symptoms are improved or resolved, as evaluated by the PI or designee, anakinra will be decreased to the prophylactic dosing (200 mg/day).

Anakinra dose modification: in patients with severe renal insufficiency or end-stage renal disease, defined as CrCl less than 30 mL/min, the anakinra dose will be reduced to 50% of the target dose (4 mg/kg/day).

Step 2 (1 mg/kg/h): In the absence of improvement or worsening of CRS or ICANS symptoms despite anakinra treatment at 8 mg/kg/day, as evaluated by the PI or designee, anakinra will be increased once to 1 mg/kg/h administered as a continuous IV infusion for 72 hours. The step 2 anakinra dose will be calculated using the participant's actual or ideal body weight as per PI discretion, rounded to the nearest 100 mg, and diluted in NaCl 0.9% at a volume sufficient to achieve a goal concentration of 1 mg/ml. After 72 hours of anakinra at 1 mg/kg/h, anakinra will be decreased to 8 mg/kg/day. Once CRS and ICANS symptoms are improved or resolved on anakinra at 8 mg/kg/day, as evaluated by the PI or designee, anakinra will be further decreased to the prophylactic dosing.

Anakinra dose modification: in patients with severe renal insufficiency or end-stage renal disease, defined as CrCl less than 30 mL/min, the anakinra dose will be reduced to 50% of the target dose (0.5 mg/kg/h).

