**Anakinra up-titration:**

[figure not shown]
Step 1 (8 mg/kg/day): In patients who develop CRS or ICANS during anakinra prophylaxis at 200 mg/day, anakinra will be increased to 8 mg/kg/day. The step 1 anakinra dose will be calculated using the participant's actual or ideal body weight as per PI discretion. The total daily dose will be divided over three doses in 24 hours, each dose will be rounded to the nearest 100 mg, diluted in NaCl 0.9%, and given IV over approximately 10-30 minutes. Once CRS and ICANS symptoms are improved or resolved, as evaluated by the PI or designee, anakinra will be decreased to the prophylactic dosing (200 mg/day).

Step 2 (1 mg/kg/h): In the absence of improvement or worsening of CRS or ICANS symptoms despite anakinra treatment at 8 mg/kg/day, as evaluated by the PI or designee, anakinra will be increased once to 1 mg/kg/h administered as a continuous IV infusion for 72 hours. The step 2 anakinra dose will be calculated using the participant's actual or ideal body weight as per PI discretion, rounded to the nearest 100 mg, and diluted in NaCl 0.9%. After 72 hours of anakinra at 1 mg/kg/h, anakinra will be decreased to 8 mg/kg/day. Once CRS and ICANS symptoms are improved or resolved on anakinra at 8 mg/kg/day, as evaluated by the PI or designee, anakinra will be further decreased to the prophylactic dosing.

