#### **Anakinra up-titration algorithm:**

## 6.2 Anakinra Drug Product

Anakinra is supplied in single use 1 mL prefilled glass syringes with 27 gauge needles as a sterile, clear, colorless-to-white, preservative-free solution for daily subcutaneous (SC) administration. Each 1 mL prefilled glass syringe contains: 0.67 mL (100 mg) of anakinra in a solution (pH 6.5) containing sodium citrate (1.29 mg), sodium chloride (5.48 mg), disodium EDTA (0.12 mg), and polysorbate 80 (0.70 mg) in Water for Injection, USP. Anakinra will be supplied by Sobi and dispensed through Investigational Drug Services.

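### On its natural reading, the Step 1 rounding rule gives a patient with CrCl below 30 mL/min and a dosing weight of 37.5 to below 56.25 kg the same 300 mg/day as a patient without renal impairment, above the stated 4 mg/kg/day (minor dosing-safety correction)

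*Combined protocol and SAP*

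**What the plan says.** Section 6.1, under the up-titration heading, sets Step 1 at 8 mg/kg/day for patients who develop CRS or ICANS on prophylaxis. On how the dose is given it says: "The total daily dose will be divided over three doses in 24 hours, each dose will be rounded to the nearest 100 mg". The synopsis repeats the rounding. The dosing weight is "actual or ideal body weight as per PI discretion".

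A separate dose-modification paragraph covers severe renal insufficiency, "defined as CrCl less than 30 mL/min, the anakinra dose will be reduced to 50% of the target dose (4 mg/kg/day"). It changes the target and nothing else. It gives no other number of doses, interval or rounding unit, and it does not exempt the reduced dose from the 100 mg rounding.

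Two other renal rules in section 6.1 give context. Prophylaxis moves from daily to every other day. At Step 2, "the anakinra dose will be reduced to 50% of the target dose (0.5 mg/kg/h").

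Section 5.2 excludes "Serum creatinine > 2.5 mg/dL" but sets no creatinine-clearance limit. Section 6.2 describes the supply as single-use syringes, each with "0.67 mL (100 mg) of anakinra in a solution".

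**The concern.** A 100 mg rounding unit is coarse for a dose of about 70 mg. The full and the halved Step 1 targets can round to the same whole syringe, and the renal reduction then disappears. The other two renal rules do halve the dose, one by doubling the interval and one by halving the infusion rate. Only Step 1 can fail in this way.

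Patients can reach the rule, because eligibility rests on creatinine and not on clearance. The choice between actual and ideal weight can also move a patient into or out of the affected band. At stake is whether a safety instruction is carried out as intended for a light patient with poor renal function.

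**Working it through.** **Inputs.** Step 1 target 8 mg/kg/day, renal target 4 mg/kg/day, three doses per 24 hours, each rounded to the nearest 100 mg (section 6.1). Syringe content 100 mg (section 6.2).

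**The plan's own figure.** 0.5 × 8 = 4 mg/kg/day, which agrees with the stated renal target.

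**Formula.** Daily dose = 3 × [target × weight / 3, rounded to the nearest 100 mg]. This assumes that the Step 1 split and rounding also apply to the renal target, and that an exact 50 mg tie rounds up.

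**Where the rounding changes.**
- Full target: 8w/3 reaches 150 mg at w = 150 × 3/8 = 56.25 kg. Below that weight the dose is 300 mg/day; from 56.25 to below 93.75 kg it is 600 mg/day.
- Renal target: 4w/3 reaches 50 mg at w = 37.5 kg and 150 mg at w = 112.5 kg. Between these weights the dose is 300 mg/day.
- Both doses are therefore 300 mg/day from 37.5 to below 56.25 kg.

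**Renal dose in the band.**

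| Dosing weight (kg) | Single dose before rounding, full / renal (mg) | Renal dose as written (mg/day) | mg/kg/day | Above 4 mg/kg/day |
|---|---|---|---|---|
| 37.5 | 100 / 50 | 300 | 8.0 | 100% |
| 40 | 106.7 / 53.3 | 300 | 7.5 | 88% |
| 45 | 120 / 60 | 300 | 6.7 | 67% |
| 50 | 133.3 / 66.7 | 300 | 6.0 | 50% |
| 56 | 149.3 / 74.7 | 300 | 5.4 | 34% |

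The value 8.0 arises only at 37.5 kg, where the renal dose is exactly 50 mg and the tie must round up.

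**Outside the band.** At 56.25 kg the renal dose is 300/56.25 = 5.33 mg/kg/day (+33%), and the full dose is now 600 mg/day, so the halving works. From there to below 131.25 kg the renal dose stays within ±33% of 4 mg/kg/day. The full Step 1 dose has a rounding error of the same size: just below 56.25 kg it is 5.33 mg/kg/day (−33% of 8), and at 56.25 kg it is 600/56.25 = 10.67 (+33%). Those weights are not part of this point.

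**Rounding the daily total instead.** 4w to the nearest 100 mg gives 200 mg/day from 37.5 to below 62.5 kg, 300 to below 87.5 kg, 400 to below 112.5 kg and 500 to below 137.5 kg. In the band this is 200/37.5 = 5.33 (+33%), 200/50 = 4.0 and 200/56.25 = 3.56 (−11%). Over 37.5 to below 131.25 kg, the deviation from target is −33% to +100% as written and −20% to +33% with this rule. The new rule is never farther from target, because every multiple of 300 mg is also a multiple of 100 mg.

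**Patients affected.** The documents give no rate. Assume that 5 to 7 of the 10 expansion patients step up, 5–15% of them have CrCl below 30 mL/min, and 10–40% have a dosing weight in the band, independently. The expected number is then 5 × 0.05 × 0.10 = 0.025 to 7 × 0.15 × 0.40 = 0.42. If light patients more often have low clearance, the number would be higher, but still small.

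**The case against.** The strongest objection is that the result depends on one reading. The rounding sentence stands in the Step 1 paragraph; the renal paragraph is silent on division and rounding. If staff halved the already rounded dose, the patient would get 150 mg/day and the problem would disappear. Applied literally, the rounding would also give 0 mg below 37.5 kg, which suggests it was not written with renal doses in mind. The up-titration figure was not visible in the text reviewed and may state renal doses. This lowers confidence but does not remove the point: the text defines the reduction on the target in mg/kg/day, before any division, and offers no other rule. If two readings lead to 150 and 300 mg/day, a clarifying sentence is still needed.

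A second objection is clinical discretion: "The anakinra dose may be modified or held at the discretion of the PI or designee". The wording is general, but it sits under the prophylactic dose, with infection as its example. It could soften the effect without correcting the calculation.

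A third is that no harm is shown. This stands. The excess at 50 kg is 300 − 200 = 100 mg/day, one syringe. The plan itself gives renal patients 0.5 × 24 = 12 mg/kg/day at Step 2, although only when Step 1 has not brought improvement.

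A reader might also infer that renal patients across the band receive 8 mg/kg/day, twice their target. The documents do not support that. The rounded full dose is itself below its target over nearly all of the band. Against the unrounded 8 mg/kg/day, 300 mg is 25% lower at 50 kg (400 mg) and about 33% lower at 56 kg (448 mg).

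**Conclusion.** The point holds as a minor dosing-safety correction, with medium confidence. On the natural reading of section 6.1, a patient with CrCl below 30 mL/min and a dosing weight of 37.5 to below 56.25 kg gets the same rounded Step 1 dose as a patient of that weight without renal impairment. The stated target is exceeded by half at 50 kg and by about a third at the top of the band.

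This rests on the unstated extension of the three-way split and 100 mg rounding to the renal target, and on the figure not saying otherwise. On the assumptions shown, fewer than one patient is likely to be affected. The primary analysis counts patients free of CRS and uses no dose information, so it is untouched. Neither a demonstrated safety hazard nor a general failure of the renal rules follows from the text.

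**What to change.** Add one sentence to Step 1 in section 6.1: *For CrCl below 30 mL/min, round the Step 1 daily total (4 mg/kg/day) to the nearest 100 mg and give it in whole-syringe doses, as two doses per day where needed.* Then check that the up-titration figure agrees. In the band this means 100 mg twice daily. Rounding each dose to 50 mg would instead give 150 mg/day, need part-syringes and fall to 2.7 mg/kg/day near 56 kg.

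The costs are:
- Some renal patients move to twice-daily dosing (200 mg/day from 37.5 to below 62.5 kg, 400 mg/day from 87.5 to below 112.5 kg).
- From 87.5 to below 112.5 kg the dose rises from 300 to 400 mg/day, closer to target.
- From 112.5 kg, 500 mg/day means unequal doses.
- In the band, the cut from the rounded non-renal dose is one third (300 to 200 mg/day), not 50%.
- A patient on 200 mg daily prophylaxis whose CrCl first falls below 30 mL/min at CRS or ICANS onset gets no increase in daily dose at Step 1 from 37.5 to below 62.5 kg. At 50 kg this is the plan's own target (4 × 50 = 200 mg). Renal patients already on every-other-day prophylaxis still step up, from an average of 100 to 200 mg/day.
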